4.4 End of Study Definition

A participant is considered to have completed the study if he/she has completed the last contact planned in the SoA.

The end of the study is defined as the date of the last contact of the last participant in the study.

However, for periodic safety reports, the study is considered completed when the Clinical Study Report (CSR) is finalized.

5 Study Population

Prospective approval of protocol deviations to recruitment and enrollment criteria, also known as protocol waivers or exemptions, is not permitted. This study is designed to be pragmatic to maximize representation of the broader population by minimizing exclusionary eligibility criteria and allowing the participation of individuals with a broad range of medical conditions, including controlled HIV infection, Hepatitis B and Hepatitis C, and conditions associated with an increased risk of severe COVID-19. It is also designed to be inclusive of other subpopulations affected by COVID-19, including older adults as well as ethnic and racial minorities.

If an approved/authorized vaccine is available in the country or region where the study is conducted, Investigators will discuss this information with prospective study participants at the time of informed consent who will be encouraged to obtain the approved/authorized vaccine if applicable to them. Recruitment of eligible participants will proceed only if, despite encouragement, the candidate participant expresses no intention to seek an authorized or approved vaccine at least until completion of the key follow-up timepoint (D43) for informing progression to Phase III and dose selection.

5.1 Inclusion Criteria

Participants are eligible for the study only if all of the following criteria are met:

I01: Aged 18 years or older on the day of inclusion^a

I02: A female participant is eligible to participate if she is not pregnant or breastfeeding and one of the following conditions applies:

- Is of non-childbearing potential. To be considered of non-childbearing potential, a female must be post-menopausal for at least 1 year or surgically sterile.

OR

- Is of childbearing potential and agrees to use an effective contraceptive method or abstinence from at least 4 weeks prior to the first vaccination until at least 12 weeks after the last vaccination (ie, second dose of primary series or booster injection).
- A participant of childbearing potential must have a negative highly sensitive pregnancy test (urine or serum as required by local regulation) within 4 hours before any dose of study intervention, see [Section 8.4.5](#) (pregnancy testing).

I03: Informed consent form has been signed and dated

I04: Able to attend all scheduled visits and to comply with all study procedures

I05: Covered by health insurance, only if required by local, regional, or national regulations

I06: SARS-CoV-2 rapid serodiagnostic test performed at the time of enrollment to detect presence of SARS-CoV-2 antibodies (Original Phase II Cohort)

^a Participants in the Comparator Group for Supplemental Cohorts 1 and 2 must be 18 to 55 years of age.

I07: For persons living with human immunodeficiency virus (HIV), stable HIV infection determined by participant currently on ARVs with CD4 count > 200/mm³

I08: Does not intend to receive an authorized/approved COVID-19 vaccine from first vaccination to 3 weeks after the second vaccination (D43) despite encouragement by the Investigator to receive the authorized vaccine available to them at the time of enrollment^a

I09: Supplemental cohorts: for participants originally enrolled in the Phase II Cohort of the study, informed consent has to be signed and dated for transitioning to Supplemental Cohort 2

I10: Supplemental Cohorts, Booster Arms: received a complete primary vaccination series^b with an authorized/conditionally approved mRNA COVID-19 vaccine (mRNA-1273 [Moderna] or BNT162b2 [Pfizer/BioNTech]) or adenovirus-vectored COVID-19 vaccine (ChAdOx1 nCoV-19 [Oxford University/AstraZeneca] or Ad26.COV2.S [J&J/Janssen]), with the last dose administered a minimum of 4 months prior to inclusion but not longer than 10 months prior to inclusion

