5.2 Exclusion Criteria

Participants are not eligible for the study if any of the following criteria are met:

E01: Participation at the time of study enrollment (or in the 30 days preceding the first study vaccination) or planned participation during the present study period in another clinical study investigating a vaccine, drug, medical device, or medical procedure

E02: Receipt of any vaccine in the 30 days preceding or on the day of the first study vaccination or planned receipt of any vaccine between the first study vaccination and in the 30 days following the second study vaccination except for influenza vaccination, which may be received at any time in relation to study intervention.

E03: Applicable to Original Phase II Cohort, Supplemental Cohort 1, Cohort 2 Comparator Group: Prior administration of a coronavirus vaccine (severe acute respiratory syndrome coronavirus 2 [SARS-CoV-2], SARS-CoV, Middle East Respiratory Syndrome [MERS-CoV])^c

^a While recruitment of eligible participants will proceed only if the candidate participant expresses no intention to seek an authorized or approved vaccine at least until completion of the key follow-up timepoint (D43), if the participant is enrolled and seeks vaccination of an authorized/approved vaccine outside of the study, he/she will be encouraged to discuss this intention proactively with the study Investigator and will be permitted to receive the authorized vaccine at any time. If the participant receives the authorized/approved vaccine, this information would be collected and the participant's data up to the point of receipt of authorized/approved vaccine will be included in the primary analysis for immunogenicity and safety. Participants will continue to be followed for the duration of the study as per scheduled visits and procedures. Participants will not receive the second vaccination if they have received the authorized/approved vaccine between the first and second scheduled vaccination (see [Section 7.1.2: Definitive Contraindications](#)).

^b To be confirmed either by official written or electronic record

^c Not applicable to booster arms in Supplemental Cohorts 1 and 2

E04: Known systemic hypersensitivity to any of the vaccine components, or history of a life-threatening reaction to a vaccine containing any of the same substances^a

E05: Dementia or any other cognitive condition at a stage that could interfere with following the study procedures based on Investigator's judgment

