E06: Self-reported thrombocytopenia, contraindicating intramuscular (IM) vaccination based on Investigator's judgment

E07: Bleeding disorder, or receipt of anticoagulants in the past 21 days preceding inclusion, contraindicating IM vaccination based on Investigator's judgment

E08: Deprived of freedom by an administrative or court order, or in an emergency setting, or hospitalized involuntarily

E09: Unstable acute or chronic illness that in the opinion of the Investigator or designee poses additional risk as a result of participation or that could interfere with the study procedures

E10: Receipt of solid-organ or bone marrow transplants in the past 180 days

E11: Receipt of anti-cancer chemotherapy in the last 90 days

E12: Receipt of immunoglobulins^b, blood, or blood-derived products in the past 3 months

E13: Moderate or severe acute illness/infection (according to Investigator judgment) on the day of vaccination or febrile illness (temperature $\geq 38.0^{\circ}\text{C}$ [$\geq 100.4^{\circ}\text{F}$]). A prospective participant should not be included in the study until the condition has resolved or the febrile event has subsided

E14: Identified as an Investigator or employee of the Investigator or study center with direct involvement in the proposed study, or identified as an immediate family member (ie, parent, spouse, natural or adopted child) of the Investigator or employee with direct involvement in the proposed study

E15: Exclusion criterion for the Supplemental Cohort 1 and Cohort 2 Comparator Group: positive rapid diagnostic test for SARS-CoV-2 antibodies at time of enrollment

E16: Exclusion criterion for Supplemental Cohort 2 CoV2 preS dTM-AS03 (D614) primed individuals (ie, primed as participant in the Original Phase II Cohort of the present study): Receipt of authorized/conditionally approved COVID-19 vaccine after enrollment in Original Phase II Cohort

E17: Exclusion criterion for all Booster Groups: Documented virologically-confirmed SARS-CoV-2 infection (by NAAT) after first dose of primary immunization

Depending on country regulations and feasibility, if the participant has a primary physician who is not the Investigator, the site may contact this physician with the participant's consent to inform him / her of the participant's participation in the study. In addition, the site may ask this primary physician to verify exclusion criteria including but not limited to previous therapies, such as previous vaccines.

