Eligible participants transitioning from the VAT00002 Original Phase II Cohort who have received the CoV2 preS dTM-AS03 (D614) candidate vaccine (targeted N = 450; actual number to be determined by number of VAT00002 participants meeting eligibility criteria for transition) will be randomized to receive a single injection of either the CoV2 preS dTM-AS03 (D614) or the CoV2 preS dTM-AS03 (B.1.351) booster vaccine. Randomization will occur by age strata (assumption that about 2/3 of participants will be 18-55 years of age (ie, 300 adults 18-55 years old, allocation ratio of 9:1 between CoV2 preS dTM-AS03 [D614] group and the CoV2 preS dTM-AS03 [B.1.351] group); the actual number and age distribution will be determined by characteristics of those who meet eligibility criteria for transition). A subset of 10% of participants aged 18-55 (~30 participants in the 2 Booster Groups combined) will be randomly assigned to collect CMI and mucosal samples plus variant testing.

Site staff will connect to the IRT system, enter the identification and security information, and confirm a minimal amount of data in response to IRT prompts. The IRT will collect information on age-group, priming vaccine, high-risk medical conditions, and ethnicity/race (the last 2 for monitoring purposes and high-risk medical conditions for potential capping). The IRT will then provide the group assignment (intervention arm and CMI/mucosal subset [if applicable]). The full detailed procedures for group allocation are described in the Operating Guidelines.

Supplemental Cohorts Comparator Group:

This Group will be open-label and not randomly assigned as all eligible participants will have common baseline characteristics (previously unvaccinated) and all will receive two injections of the CoV2 preS dTM-AS03 (D614) candidate vaccine 21 days apart. Eligible participants must be 18-55 years of age and have a negative baseline SARS-CoV-2 rapid serodiagnostic test to be enrolled into this group. A subset of 5% of participants aged 18-55 (~26 participants) will be randomly assigned to variant testing subsets.

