Per-protocol analysis set (PPAS)	Subset of the FAS. Participants presenting with at least 1 of the following criteria will be excluded from the PPAS: 
• Participant did not meet all protocol-specified inclusion criteria or met at least one of the protocol-specified exclusion criteria• Participants did not receive both injections for 2 doses primary vaccination groups or 1 dose booster injection for booster vaccination groups• Participant received a vaccine other than the one that he / she was randomized to receive• Preparation and / or administration of vaccine was not done as per-protocol• Participant did not receive protocol defined vaccine in the proper time window• Participants who did not provide all post-dose blood samples within the proper time window or no post-dose blood sample was drawn• Participant received the second injection (in the primary vaccination groups) despite meeting any of the definitive contraindication criteria• Participant receives an authorized/approved COVID-19 vaccine prior to D36 for primary vaccination groups or D15 for booster vaccination groups The definition may be complemented with additional criteria for exclusion after the review of protocol deviations reported on site.

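### Inclusion criterion I10, as worded, bars every participant primed with the study vaccine from the booster arms that the protocol plans for them, and from the per-protocol test at step (b) of the D614 sequence

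*Protocol*

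**What the plan says.** **Eligibility.** Section 5 opens with the rule "Prospective approval of protocol deviations to recruitment and enrollment criteria, also known as protocol waivers or exemptions, is not permitted". Section 5.1 then states "Participants are eligible for the study only if all of the following criteria are met". I10 reads "I10: Supplemental Cohorts, Booster Arms: received a complete primary vaccination series^b with an authorized/conditionally approved mRNA COVID-19 vaccine", goes on to name two mRNA and two adenovirus-vectored products, and sets the interval since the last dose. The sponsor's protein vaccine is not on the list, and I10 carries no limit to particular priming strata.

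**Planned enrollment.** Section 6.3.1 makes the study vaccine the fifth priming stratum of the Cohort 2 Booster Groups and provides for "Eligible participants transitioning from the VAT00002 Original Phase II Cohort who have received the CoV2 preS dTM-AS03 (D614) candidate vaccine (targeted N = 450"). The Synopsis (description of the Supplemental Phase III Cohorts) and Table 4.1 describe the same group, and Table 4.3 gives its numbers. The group has its own consent criterion, "I09: Supplemental cohorts: for participants originally enrolled in the Phase II Cohort of the study, informed consent has to be signed and dated", and its own exclusion, E16: "Receipt of authorized/conditionally approved COVID-19 vaccine after enrollment in Original Phase II Cohort".

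**Analysis.** Section 9.3 lists as a ground for removal from the PPAS: "Participant did not meet all protocol-specified inclusion criteria or met at least one of the protocol-specified exclusion criteria". Section 9.4.2.2.3 uses the PPAS for the secondary immunogenicity objectives and evaluates the full analysis set (FAS) as well. Section 9.1.2 places the protein-primed group at step (b) of the D614 testing sequence, directly after the Pfizer-primed co-primaries.

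**The concern.** I10 asks these participants for something that other criteria forbid them to have. At stake are the status of a planned stratum and the working of a gatekeeping step. If sites follow I10, nobody in the stratum can be enrolled. If sites follow Section 6.3.1 instead, every protein-primed participant carries an inclusion-criterion failure, which by Section 9.3 removes them from the PPAS. Keeping them would mean setting aside a written PPAS exclusion at the step that controls all later D614 claims. Section 9.3 allows exclusion criteria to be added after the review of protocol deviations, but does not provide for dropping one.

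**Working it through.** **1. Can a protein-primed participant meet I10 by another route?**

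- Before Phase II entry: no. E03 (Section 5.2) excluded anyone with a prior coronavirus vaccine from the Original Phase II Cohort.
- After Phase II entry: no. E16 excludes anyone who then received an authorized or conditionally approved vaccine.
- Through I09: no. It adds a transition consent and gives no exemption from I10.
- By falling outside the term booster arms: no. Table 6.2 assigns the 5 µg D614 product to the booster arms of Cohorts 1 and 2, and in Cohort 2 only protein-primed participants receive D614 (Table 4.3).

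E03 and E16 are both needed. E16 alone closes only the period after Phase II enrollment.

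**2. How many are affected (Table 4.3)?**

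- D614 booster: 270 (18-55 years) + 75 (56 and older) = 345.
- B.1.351 booster: 30 + 75 = 105.
- Total: 345 + 105 = 450, and 450/3660 = 12.3%.
- In a hypothesis test: only the 270 aged 18-55 on D614, and 270/3660 = 7.4%. The other 180 are described only.

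**3. What does the stated step (b) power presume?** Table 9.1 gives non-inferiority 99.7%, superiority above 99.9%, overall 99.6%. Inputs from Section 9.2.2: one-sided alpha 0.025/3 = 0.00833; log10 SD 1.0 (booster) and 0.65 (comparator); true GMT ratio 1.5 against margin 1/1.5; true post/pre ratio 5 against margin 2, with SD 1.0; attrition 3% (booster) and 10% (comparator).

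- Evaluable: 270 × 0.97 = 261 (rounded down); 515 × 0.90 = 464 (rounded).
- Non-inferiority: difference = log10(1.5) − log10(1/1.5) = 0.352; SE = √(1.0²/261 + 0.65²/464) = 0.0689; ratio 5.11. The normal approximation gives Φ(5.11 − 2.39) = 99.67%. The unequal-variance noncentral t gives 99.65%.
- Superiority: log10(5/2) = 0.398; SE = 1.0/√261 = 0.0619; ratio 6.43; power 99.997% (paired t).
- Overall: 0.99655 × 0.99997 = 99.65%.

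The stated figures are reproduced to within 0.1 percentage point. The same method gives 98.7%, 99.8%, 94.1%, 80.6% and 84.5% for the other GMT non-inferiority rows, against 98.7%, 99.8%, 94%, 80.5% and 84.5% stated. I make no use of the seroresponse power rows. The 99.6% is therefore sound, provided about 270 eligible protein-primed participants exist. Under I10 as written, none are eligible.

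**4. What does step (b) gate (Section 9.1.2)?**

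| Step, D614 candidate | Tests | Stated overall power | I10 applied literally |
|---|---|---|---|
| (a) Pfizer-primed co-primaries | 2 | 98.7% | unaffected |
| (b) protein-primed | 2 | 99.6% | no PPAS participants |
| (c) pooled mRNA-primed | 2 | 99.8% | blocked by (b) |
| (d) pooled adenovirus-primed | 2 | 93.2% | blocked by (b) |
| (e) seroresponse, four groups in turn | 4 | not used here | blocked by (b) |

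The B.1.351 and bivalent sequences contain no protein-primed step, and each has its own 0.025/3.

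**The case against.** The strongest reply is that I10 was never meant for this group. Section 5.1 is a composite list that has to be read by relevance. I08, for example, has no cohort limit yet refers to a second vaccination that no booster arm receives. The footnote to I10 asks for an official record of the priming series, which suits vaccination outside the study better than doses given within it. I09, E16, the fifth priming stratum and the sample size tables all presuppose that protein-primed participants enroll. This stands as evidence of intent. It does not change the text that sites and the PPAS review must apply, and no section limits I10.

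Three stronger readings are tempting and not supported:

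- A reader might infer that the per-protocol power of step (b) is zero. That is not an estimate of what will happen. It follows only if these participants are randomized in a named stratum and then all removed for failing I10, and nothing in the protocol says the sponsor intends that. The FAS would keep everyone randomized and injected, although only as a supportive evaluation.
- A reader might infer that the loss bears on inference for all 450, or on the trial's main conclusions. Only 270 enter a test, and that test is a conditional secondary one for one of three candidates.
- A reader might infer that the interim trigger in Section 9.5 must change too. Its conditions refer to primary immunogenicity data, the protein-primed test is a conditional secondary one, and the scope of I10 has no bearing on it.

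**Conclusion.** The point holds as an internal contradiction. I10 conflicts with the planned enrollment in the Synopsis, Tables 4.1 and 4.3 and Section 6.3.1, and E03 with E16 leaves no way to satisfy it. All of the roughly 450 planned protein-primed participants fail the written criteria. For testing, the effect is confined to 270 participants at step (b) and to the steps of the D614 sequence that depend on it. The co-primary objectives and the other two candidates are untouched. The blocked sequence rests on three assumptions: I10 is applied literally, no waiver is given, and the PPAS rule is followed as written. With I10 read as evidently intended, the stated power stands. Because following the text exactly gives a result that the sponsor plainly does not want, the wording should be corrected and not left to interpretation.

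**What to change.** Limit I10 to participants primed with an mRNA or adenovirus-vectored vaccine. Add a matching inclusion criterion for participants transitioning from the Original Phase II Cohort, based on their priming there with the study vaccine. Section 5 states a priming interval only inside I10, while the Synopsis and Table 4.1 state one for this group directly. The new criterion must be reconciled with those passages, and this review does not propose the interval. If any protein-primed participants have already been enrolled, record before the database lock how I10 is to be read for their PPAS status.

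The cost is one re-scoped criterion and one added criterion. Arms, sample sizes, visits, alpha and testing order stay as they are, and Section 9.5 needs no change on this account.

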At present, there is limited evidence as to the durability of efficacy beyond the 2 to 6 months following the completion of the primary series of vaccines that have received emergency use authorization or conditional approval. While the evidence to define a correlate of risk or correlate of protection is not yet fully matured, modelling shows a strong correlation between efficacy and peak neutralizing antibody titers ([62](#)) ([63](#)). Furthermore, extensions of such modelling allow for prediction of the effects of waning immunity on efficacy. For mRNA-1273, one authorized COVID-19 vaccine for which post-vaccination functional antibody titers up to a half-year have been published, neutralizing antibody levels against the prototype strain decline by 4- to 7-fold at

6 months from the peak titers achieved post-vaccination (64). Modelling predicts the loss-of-efficacy impact would be magnified against variants with larger reductions in neutralizing activity compared to the prototype strain, thus implying the need for an earlier booster dose. Given these uncertainties, this study will evaluate the administration of booster doses among individuals who received a primary series with an authorized COVID-19 vaccine starting 4 to 10 months previously.

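### No eligibility criterion excludes mRNA- or adenovirus-primed volunteers who have already had a further COVID-19 dose, so already-boosted people can enter the booster arms and stay in the PPAS.

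*Protocol*

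**What the plan says.** For the mRNA- and adenovirus-primed booster arms, I10 in Section 5.1 asks that the volunteer "received a complete primary vaccination series", "with the last dose administered a minimum of 4 months prior to inclusion but not longer than 10 months prior to inclusion". The series must be confirmed from an official record.

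The criteria in Section 5.2 that touch on earlier exposure are:

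- E02: "Receipt of any vaccine in the 30 days preceding or on the day of the first study vaccination" (influenza vaccine excepted).
- E03, prior coronavirus vaccine, whose footnote reads "Not applicable to booster arms in Supplemental Cohorts 1 and 2".
- E16, for volunteers primed in the Original Phase II Cohort only: "Receipt of authorized/conditionally approved COVID-19 vaccine after enrollment in Original Phase II Cohort".
- E17, for all Booster Groups: "Documented virologically-confirmed SARS-CoV-2 infection (by NAAT) after first dose of primary immunization".

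I08 is about intentions after enrolment, not past doses. Section 4.3 says that the study will evaluate boosters in people who "received a primary series with an authorized COVID-19 vaccine starting 4 to 10 months previously". Table 1.2 collects previous COVID-19 vaccination at V01 but links it to no eligibility decision. The PPAS in Section 9.3 removes people who fail a written inclusion or exclusion criterion.

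**The concern.** I10 sets a minimum: the series must be complete and must fall in a time window. It sets no maximum on doses. A volunteer who completed the series and later had another authorized dose can satisfy every criterion.

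At stake are the co-primary and conditional tests. An extra dose would plausibly raise the D15 titre, which makes non-inferiority to the naive two-dose comparator easier to show. It would also plausibly raise the D01 titre, which shrinks the post/pre ratio tested against 2. The two co-primaries are then pushed in opposite directions by something that is not the study booster. If the extra dose came from another platform, the mRNA and adenovirus groups in the conditional objectives also become less clear.

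**Working it through.** **Step 1: does any criterion close the gap?** Take a volunteer primed with an authorized mRNA or adenovirus vaccine who has had one further dose.

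- *Last dose read as the last dose of the primary series* (the natural grammar of I10, and in line with Section 4.3). Series completed 9 months ago, extra dose 31 days ago: I10 is met, and E02 bars only 30 days. Eligible.
- *Last dose read as the last COVID-19 dose of any kind.* Series completed 14 months ago, extra dose 5 months ago: I10 is met. Eligible, and the extra dose must be at least 4 months old.
- E03 does not apply, E16 does not apply, E17 concerns infection, and I08 looks forward.
- The PPAS does not help, because no criterion was failed. Its separate rule on an authorized vaccine received before D15 cannot be meant for doses before enrolment, since it would then remove every mRNA- and adenovirus-primed participant.

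The gap exists under both readings. Only the shortest possible interval differs.

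**Step 2: reproduce the plan's power.** Inputs from Section 9.2.2: one-sided alpha 0.025/3 = 0.00833 (z = 2.394); log10 SDs of 1.0 (booster) and 0.65 (comparator); attrition of 3% and 10%; non-inferiority margin 1/1.5; post/pre margin 2 with assumed ratio 5. Evaluable numbers for Cohort 2 Pfizer-primed against the comparator are 515 × 0.97 ≈ 499 and 515 × 0.90 ≈ 463.

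- SE = √(1.0²/499 + 0.65²/463) = 0.0540.
- Non-inferiority at a true ratio of 1: log10(1.5)/0.0540 = 0.1761/0.0540 = 3.26. A noncentral t with Welch degrees of freedom gives 80.5%. Table 9.1 states 80.5%.
- The Cohort 1 Pfizer-primed arm (N = 215, about 208 evaluable) gives 98.7% for non-inferiority at a true ratio of 1.5 and above 99.9% for superiority, as stated.

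**Step 3: illustrate the effect.** Let f be the share already boosted and k their D15 titre multiple. The documents give neither, so both are assumptions. SDs are held at the plan's values. The mean log10 titre shifts by f × log10(k). If the ratio among never-boosted people is exactly 1/1.5, the chance of declaring non-inferiority is 1 − Φ(2.394 − f·log10(k)/0.0540).

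| f | k | shift | shift/SE | false claim, Cohort 2 |
|---|---|---|---|---|
| 0 | – | 0 | 0 | 0.8% |
| 10% | 2 | 0.0301 | 0.56 | 3.3% |
| 10% | 3 | 0.0477 | 0.88 | about 6.5% |
| 20% | 2 | 0.0602 | 1.11 | 10.0% |

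For the smaller Cohort 1 arm (n = 208) with k = 2, the t-based figures are 2.3% at f = 10% and 5.5% at f = 20%.

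**Step 4: post/pre ratio.** Assume that boosted entrants rise 1.5-fold instead of 5-fold. At f = 20% the ratio is 5^0.8 × 1.5^0.2 = 3.93. Superiority power with n = 208 goes from above 99.9% to 99.5% (f = 10%), 96.5% (20%) and 85.5% (30%). With n = 499 it is still 99.9% at f = 30%.

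**The case against.** The strongest reply has several parts, and some of it stands.

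- *The interval.* A reader might infer that people boosted 31 days earlier are plainly admitted. That holds only under one reading of I10. A site that sees a recent COVID-19 dose on the official record could reasonably treat the person as outside the window, and the shortest interval is then 4 months. The gap remains, but 31 days is not its settled size.
- *The intended population.* A reader might infer that the objectives and the post/pre planning ratio are confined to people with a primary series only. They are not. The objectives speak only of previous vaccination with a named vaccine or platform, and Section 9.2.2 takes the ratio of 5 from previously infected participants in the Original Phase II Cohort. The intent rests on Section 4.3 and on the way E16 and E17 control later exposure.
- *E16 as a parallel.* E16 answers a specific situation, since Original Cohort participants were free to take an authorized vaccine, and Section 5 favours few exclusions. So the omission elsewhere is not proven to be an oversight. Still, the protocol gives no reason to screen one priming group for an extra dose and not the others.
- *Strata.* A reader might infer that an adenovirus-primed, mRNA-boosted person would be counted as adenovirus-primed. Section 6.3.1 uses the priming vaccine, but for the Cohort 2 main arms Section 4.1 uses the vaccine received 4 to 10 months earlier. The classification is unclear.
- *Size.* The share and the titre multiple are assumed, and the false-claim rates apply at the null boundary, while the plan expects a true ratio of 1 or 1.5. Both co-primaries must succeed, and the second is made harder. On the figures above, however, superiority keeps high power at f = 20%, so it would do little to offset an easier non-inferiority result.

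**Conclusion.** The point holds. As written, an mRNA- or adenovirus-primed volunteer who has had an extra COVID-19 dose is eligible for the booster arms and for the PPAS under either reading of I10. That conflicts with the population described in Section 4.3 and is out of step with E16 and E17.

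The direction of the effect is plausible: easier non-inferiority, a compressed post/pre ratio and less distinct platform groups. Its size cannot be taken from the protocol, and the illustrative figures show only that a modest share of boosted entrants would matter if the true ratio sat at the margin. No claim is made about how many such people would enrol. Planned sample sizes and powers are unaffected. This should be corrected, because it concerns who enters the primary tests and not only a matter of wording.

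**What to change.** 1. State in I10 that the last dose is the final dose of the primary series.
2. Add an exclusion parallel to E16 for all mRNA- and adenovirus-primed booster arms: receipt of any COVID-19 vaccine dose beyond the primary series named in I10.
3. For anyone already enrolled with an extra dose, use the V01 vaccination history to exclude them from the PPAS for the primary and conditional objectives, keep them in the FAS and describe them separately. This must be fixed before the relevant database lock. Section 9.4 already foresees an amended SAP before that point. Decided later, it would be a post hoc change to the primary analysis set.

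The cost is one criterion, one clarification and one PPAS line in an amendment, with no new data collection. Recruitment may be somewhat slower where extra doses are common, and the PPAS may be slightly smaller.
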